## 10.5 Methods of Analysis

### 10.5.1 Primary Efficacy Analysis

Efficacy analyses for the co-primary and secondary endpoints will be based on the FAS population.

The first co-primary efficacy endpoint of the proportion of subjects who are free from headache pain at 2 hours after the first dose of study drug taken for a migraine attack with moderate to severe headache pain during the DB1 period, will be analyzed using Fisher's exact test. The

second co-primary efficacy endpoint of the proportion of subjects who are free from their Screening MBS among nausea, photophobia, and phonophobia at 2 hours postdose during the DB1 period will be similarly analyzed using Fisher's exact test. A subject's MBS will be obtained at Screening via Migraine History assessment and, for the analysis of the co-primary endpoint, that symptom must be present predose but does not have to be designated as the MBS at predose.

Analyses will be performed using the last observation carried forward (LOCF) and observed data in the FAS population and PP population.

#### **10.5.2 Secondary Endpoint Analysis**

The analysis and presentation of the secondary efficacy endpoints will be described in the SAP.

#### **10.5.3 Exploratory Analysis**

Exploratory analyses based on predose pain level and predose MBS are planned and details will be provided in the SAP.

#### **10.5.4 Subgroup Analysis**

Subgroup analyses will be performed as needed, and details will be documented in the SAP.

#### **10.5.5 Additional Efficacy Analyses**

Other possible analyses and further statistical details, if applicable, will be provided in the SAP.

#### **10.5.6 Safety Analysis**

All AEs will be coded using the latest version of the Medical Dictionary for Regulatory Activities (MedDRA) version 19.0 or higher. A TEAE is an AE with a start date on or after the initial dose of study drug and up to 5 days after the last dose of study drug. Only TEAEs will be included in summary tables. Migraine headaches will not be captured as AEs. Migraine headaches will be captured by the subject in the eDiary provided to them at screening. The information will then be entered into the appropriate eCRF page.

The incidence of all TEAEs will be tabulated by treatment received. These TEAEs will be classified by system organ class (SOC) and preferred term (PT). For incidence reporting, if a subject reported more than one AE that was coded to the same SOC or PT, the subject will be counted only once for that specific SOC or PT.

An overview of AEs, which includes subject incidence of TEAEs, headache or migraine-related TEAEs, study drug-related TEAEs, and SAEs, will be presented. The subject incidence of TEAEs, headache- or migraine-related TEAEs, study drug-related TEAEs, and SAEs will be summarized by SOC and PT.

Treatment-emergent adverse events will also be summarized in a table by severity. For TEAEs presented by severity, the worst severity during the study will be presented for each subject, SOC, and PT.

Treatment-emergent adverse events will also be summarized in a table by relationship to study drug. For TEAEs presented by relationship to study drug, the strongest relationship to study drug during the study will be presented for each subject, SOC, and PT.

All AEs will also be presented in a by-subject data listing.

All prior and concomitant medications will be classified using the Anatomical Therapeutic Chemical (ATC) classification and preferred drug names from the World Health Organization Drug Dictionary (WHO-DD), version March 2016 or later. Medications will be considered concomitant if they were taken at any time between the date of first dose and the date of last dose of study drug, inclusive. Medications will be considered as prior if stopped before the date of first dose of study drug during the DB1 period.

Prior and concomitant medications will be summarized in separate tables by ATC level 2 and preferred drug name for the safety population.

One combined listing will be provided for prior and concomitant medications. An identifier will be provided to show if a medication is prior or concomitant.

Electrocardiograms, clinical laboratory data, and vital signs measurements will be summarized by treatment group and time point along with the change from baseline (V2). During the DB period, V2 will be considered as baseline, (i.e., the visit occurring just before treatment). If a subject misses a V2 assessment but has a V1 assessment, V1 will be considered as baseline. All ECG data, clinical laboratory data, vital signs, physical examinations, study drug use, and concomitant medication use will also be presented in by-subject data listings.

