#### ***Reporting of Serious Adverse Events***

Subjects should report all SAEs that occur during the clinical study, or within 30 days of receiving the last dose of study drug, to the Investigator. It is the responsibility of the Investigator to follow the procedures described below, whether or not the SAE is considered to be related to the study drug.

At the first occurrence of an SAE, the Investigator should complete an SAE report and notify the Sponsor within 24 hours of occurrence of the SAE. An SAE report consists of the SAE form, the concomitant medication form, and any available supporting documentation (e.g., hospital discharge summary). A copy of the SAE form must be emailed **within 24 hours** to the attention of [REDACTED] at:

[name] Inc.

Fax: [REDACTED]

Email: [REDACTED]

The Investigator should not wait to receive additional information to fully document the event before notification of an SAE, though additional information may be requested. Where applicable, information from relevant laboratory results, hospital case records, and autopsy reports should be obtained.

Instances of death, congenital abnormality, or an event that is of sufficient clinical concern to influence the overall assessment of safety, if brought to the attention of the Investigator at any time after cessation of study drug administration and linked by the Investigator to this study, should be reported to the study Medical Monitor and the Sponsor.

The Sponsor and/or [REDACTED] will promptly notify all relevant parties of findings that could adversely affect the safety of subjects, influence subjects' desire to continue in the study, impact the conduct of the study, or alter the Institutional Review Board (IRB) approval of the study. In addition, [REDACTED], on behalf of the Sponsor, will expedite the reporting to all concerned Investigators and to the IRB (where required) of all adverse reactions that are both serious and unexpected. The Sponsor will expedite the reporting of all adverse reactions that are both serious and unexpected and for which there is a reasonable possibility of their being caused by the study drug, to the regulatory authorities as soon as possible but in no case later than 15 calendar days after becoming aware of their occurrence through an IND Safety Report 21 CFR 320.31(d)(3).

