### 2.2. TIMINGS OF ANALYSES

The primary analysis of safety and efficacy is planned after all subjects complete the final study visit or terminate early from the study and all relevant study data have been processed and integrated into the final locked data base.

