### **9.3. ADVERSE EVENTS**

All AEs will be coded using the Medical Dictionary for Regulatory Activities (MedDRA; version 19.0 or higher). Migraine headaches will not be captured as AEs. Migraine headaches will be captured by the subject in the eDiary provided to them, and the information will be entered into the appropriate eCRF page.

All AEs will be listed by subject. The following listings of AEs will be provided:

- All AEs
- Study-drug related AEs
- Serious adverse events (SAEs)
- AEs leading to death
- Adverse events leading to study-drug termination

Only TEAEs will be included in summary tables. Summaries for AEs will be presented for the SS, SS1, and SS2. An overall summary table of TEAEs will be produced for the following categories:

- Any TEAE
- Study-drug related TEAEs
- Serious TEAEs
- TEAEs leading to study-drug termination
- TEAEs leading to death

All TEAEs will be classified by system organ class (SOC) and preferred term (PT). Frequency count and the number of unique subjects of a TEAE will be tabulated by treatment(s) received. For the number of unique subjects reporting, if a subject reported more than one AE that was coded to the same SOC or PT, the subject will be counted only once for that specific SOC or PT.

The following summaries of TEAEs will also be provided:

- TEAEs by SOC and PT
- Study-drug related TEAEs by SOC and PT
- Serious TEAEs by SOC and PT
- TEAEs by maximum severity (mild, moderate, severe or missing) by SOC and PT
- TEAEs by strongest causality relationship (not related, possibly related, probably related, definitely related or missing) by SOC and PT

For TEAEs presented by relationship to study treatment(s), the strongest relationship to study treatment(s) during the study will be presented for each subject if coded to the same SOC or PT. For TEAEs presented by severity, the worst severity during the study will be presented for each subject if coded to the same SOC or PT. TEAEs with missing causality will be counted as related. TEAEs with missing severity will be counted as severe. The same will be true in the individual summaries.

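### SAEs and fatal events that begin more than 5 days after a dose enter no summary table by treatment, although the protocol orders an SAE summary and asks for SAE reports for 30 days after the last dose

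*Protocol*

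**What the plan says.** Protocol 10.5.6 defines a TEAE as an AE that starts between the initial dose and a limit of "up to 5 days after the last dose of study drug". It then states: "Only TEAEs will be included in summary tables". Further down it orders an AE overview and says: "The subject incidence of TEAEs, headache- or migraine-related TEAEs, study drug-related TEAEs, and SAEs will be summarized by SOC and PT". Three of the four items in that list carry the TEAE label; SAEs do not.

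Protocol 9.2.2.7 sets the reporting period: "Subjects should report all SAEs that occur during the clinical study, or within 30 days of receiving the last dose of study drug". The investigator must act on each report whether or not the event is thought related to study drug. Protocol 9.2.2.6 has AEs documented on the eCRF from consent through V4/ET.

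SAP 9.3 keeps the TEAE-only rule. Its overview has rows for serious TEAEs and for "TEAEs leading to death", and its detailed summaries include "Serious TEAEs by SOC and PT". It plans no table of all SAEs or of all fatal events. It does plan by-subject listings of all AEs, of SAEs and of AEs leading to death, none limited to TEAEs. SAP 6.2.5 gives two TEAE windows: the DB1 window closes 5 days after the DB1 dose or at the DB2 dose if that is earlier, and the DB2 window runs from the DB2 dose to 5 days after it. Protocol 10.1 gives the SAP precedence where the two differ.

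On timing, SAP 2.2 says: "The primary analysis of safety and efficacy is planned after all subjects complete the final study visit or terminate early from the study". It adds that the relevant data must be in the locked database.

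**The concern.** An SAE summary without a TEAE limit and a rule that only TEAEs enter tables cannot both be followed. The SAP resolves this by narrowing the SAE table, and SAP section 11, which lists departures from the protocol, mentions neither that narrowing nor the split of the TEAE window by period. The overview table is the one likely to be quoted as the trial's SAE and death incidence by arm. As planned, it would leave out events that the protocol tells sites to report, including some that occur while the subject is still in the study between the two doses. Protocol 9.2.2.8 names heart attack, stroke and gastrointestinal bleeding among celecoxib's warnings. With few serious events expected, one omitted event can be the difference between a row of zero and a row that is not zero.

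**Working it through.** **Inputs.** TEAE limit: 5 days after the last dose (Protocol 10.5.6), applied per period in SAP 6.2.5. SAE reporting limit: 30 days after the last dose (Protocol 9.2.2.7). V3: 2 to 7 days after the DB1 dose, with DB2 drug to be used within 4 weeks, that is 28 days (Protocol Table 9-1). V4: 2 to 7 days after the DB2 dose (Protocol 9.2.1.4). Planned size: 600 randomised with 15% dropout (Protocol 10.7). The plan states no figure of its own to reproduce.

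**1. After the last dose.** Reportable but outside the tables: 30 − 5 = 25 days. Share: 25/30 = 83% of the reporting window, counted in days.

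**2. Between the doses.** Latest DB2 dose: 7 + 28 = 35 days after the DB1 dose. The DB1 window closes at day 5 and the DB2 window opens with the DB2 dose. Onset on days 6 to 34, at most 34 − 6 + 1 = 29 days, can fall in neither. If the DB2 dose comes by day 5 there is no gap. The protocol's single window, from the initial dose to 5 days after the last, would count all these events. An event that begins in the gap and then worsens in severity within the DB2 window does count as a DB2 TEAE.

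**3. Where each kind of event appears.**

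| Event | Table by treatment (SAP 9.3) | Listing |
|---|---|---|
| SAE with onset by day 5 after a dose | Yes | Yes |
| SAE with onset from day 6 after the DB1 dose until the DB2 dose | No | Yes |
| SAE with onset on days 6–30 after the last dose | No | If it reaches the database |
| Later death from an event that began by day 5 | Yes | Yes |
| Fatal event with onset on days 6–30 after the last dose | No | If it reaches the database |

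The caveat on listings arises because eCRF documentation of AEs ends at V4/ET. Later SAEs go to the sponsor on SAE forms, and the documents do not say whether those enter the clinical database.

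**4. Window still open at V4.** 30 − 7 = 23 to 30 − 2 = 28 days.

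**5. Illustration of numbers.** The documents give no SAE rate. Assume 2% to 6% per person-year, constant over time, and 600 × 0.85 = 510 to 600 subjects dosed. Expected SAEs = n × days/365 × rate.

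- Days 6–30 after the last dose: 510 × 25/365 × 0.02 = 0.70 to 600 × 25/365 × 0.06 = 2.47.
- Days 0–5 after the last dose: 510 × 5/365 × 0.02 = 0.14 to 600 × 5/365 × 0.06 = 0.49.

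These are totals over both arms. The gap between doses is not included, because its length depends on when attacks occur.

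**The case against.** The case for leaving the plan alone has several parts.

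- **Reading in order.** Protocol 10.5.6 states the TEAE-only rule first, so the later mention of SAEs can be taken to mean serious TEAEs, and SAP 9.3 then only clarifies. This is a possible reading, and it weakens the charge of an undeclared change to the SAE table. It does not cover SAP 6.2.5, which differs from the protocol's single window and drops events between doses that the protocol would count.
- **Convention.** The 5-day limit is used consistently and suits a trial with one dose per period. That stands: the serious-TEAE tables should stay. The gap is that nothing by treatment sits beside them.
- **Listings.** A reader might infer that late SAEs and deaths disappear altogether. The documents do not support that, because SAP 9.3 lists SAEs and AEs leading to death without a TEAE limit. What is missing is incidence by treatment and, for events after V4/ET, assurance that the report reaches the listing.
- **Deaths.** A reader might also infer that any late death is left out. The test is onset of the event, not date of death.
- **Small numbers and passive reporting.** Neither the present tables nor a fuller one could support a formal comparison of arms. After V4 no visit is scheduled and reports come unsolicited, so 83% is a share of days in a largely passive window, not of scheduled collection. Both points stand and limit the weight of the finding.
- **Lock timing.** It is tempting to conclude that the analysis must wait 30 days after the last dose. SAP 2.2 already waits for the relevant data, and that may include the 30-day SAE reports. The text does not say.

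**Conclusion.** The point holds as a gap in tabulation. Under the SAP as written, SAEs and fatal events with onset on days 6–30 after the last dose (25 of 30 reporting days), and those with onset from day 6 after the DB1 dose until the DB2 dose (at most about day 35), are counted in no summary table by treatment. This assumes that the tables for the overall Safety Set combine the two windows of SAP 6.2.5, since the SAP gives no third definition. The number of events affected cannot be computed from the documents. The illustration of about 0.7 to 2.5 events after the last dose rests entirely on an assumed rate. It suggests that the trial's safety conclusion is unlikely to turn on this, but that the SAE and death rows by arm could be incomplete. The correction is inexpensive and worth making.

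**What to change.** In SAP 9.3, and in Protocol 10.5.6 if it is amended, make SAEs and deaths an exception to the TEAE-only rule. Add a table, overall and by SOC and PT, of all SAEs and all AEs leading to death with onset from the first dose through 30 days after the last dose. Assign each event to the most recent treatment received before onset, and state the denominators. Keep the serious-TEAE tables alongside. State that SAE reports received after V4/ET are included, and record the change in SAP section 11 together with the per-period TEAE definition. In SAP 2.2, say whether the relevant study data include the 30-day SAE reports; a fixed lock delay is not required.

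The cost is one or two small extra tables, and a step to bring SAE reports received after V4/ET into the database if they do not already go there. The counts will include some background events, and a footnote should say that ascertainment after V4/ET is passive.

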#### **10.6 Interim Analyses**

No interim analysis is planned.

#### **10.7 Determination of Sample Size**

Approximately 600 subjects will be randomized for the DB1 period. Subjects who discontinue participation without completing the study protocol will not be replaced.

The first co-primary endpoint is the comparison of the proportion of subjects who are pain-free at 2 hours after the first dose of study drug. It is assumed that 17.6% of placebo and 29.2% of DFN-15 (treated) subjects will be pain-free at 2 hours. A sample size of 600 subjects will provide 88% power to detect this assumed difference between placebo and DFN-15 at a 5% (2-sided) level of significance and with a 15% dropout rate.

The second co-primary endpoint is the comparison of the proportion of subjects who are free from their Screening MBS among nausea, photophobia, and phonophobia at 2 hours after the first dose of study drug. It is assumed that 28.2% of placebo and 44.7% of DFN-15 (treated) subjects will be free from their Screening MBS at 2 hours. A sample size of 480 subjects will provide 94% power to detect this assumed difference between placebo and DFN-15 at a 5% (2-sided) level of significance and with a 15% dropout rate.

Since the sample size for the first co-primary endpoint is larger than that of the second co-primary endpoint, the larger sample size will be used for the study.

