### 3.5. DETERMINATION OF SAMPLE SIZE

Approximately 600 subjects will be randomized for the DB1 treatment period. Subjects who discontinue participation without completing the study protocol will not be replaced.

The first co-primary endpoint is the comparison of the proportion of subjects who are pain-free at 2 hours after the first dose of study drug. It is assumed that 17.6% of

placebo and 29.2% of DFN-15 (treated) subjects will be pain-free at 2 hours. A sample size of 600 subjects will provide 88% power to detect this assumed difference between placebo and DFN-15 at a 5% (2-sided) level of significance and with a 15% dropout rate.

The second co-primary endpoint is the comparison of the proportion of subjects who are free from their Screening MBS among nausea, photophobia, and phonophobia at 2 hours after the first dose of study drug. It is assumed that 28.2% of placebo and 44.7% of DFN-15 (treated) subjects will be free from their Screening MBS at 2 hours. A sample size of 480 subjects will provide 94% power to detect this assumed difference between placebo and DFN-15 at a 5% (2-sided) level of significance and with a 15% dropout rate.

Since the sample size for the first co-primary endpoint is larger than that of the second co-primary endpoint, the larger sample size will be used for the study.

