## 8. EFFICACY

### 8.1. CO-PRIMARY EFFICACY ENDPOINTS AND ANALYSES

#### 8.1.1. Primary Analyses of the Co-Primary Endpoints

The first co-primary efficacy endpoint is the proportion of subjects who are pain-free 2 hours postdose compared between DFN-15 and placebo in the DB1 treatment period (defined as a reduction from predose moderate [Grade 2] or severe [Grade 3] pain to none [Grade 0]).

The second co-primary efficacy endpoint is the proportion of subjects who are free from their Screening MBS among nausea, photophobia, and phonophobia at 2 hours postdose compared between DFN-15 and placebo in the DB1 treatment period. A subject's Screening MBS is obtained at Screening via Migraine History assessment, and for the analysis of the co-primary endpoint that Screening MBS symptom must be present at predose but it does not have to be designated as the MBS at predose.

To test for statistical significance of the co-primary efficacy endpoints, the closed sequential testing procedure will be utilized. If the first co-primary endpoint is statistically significant at a two-sided 0.05 level of significance, the second co-primary endpoint will be tested at a two-sided 0.05 level of significance. The study must show a significant statistical beneficial experimental treatment effect for both co-primary endpoints to be considered statistically successful, controlling the significance level at 0.05. Since statistical significance with both co-primary endpoints is required to declare trial success, multiplicity due to multiple primary endpoints is a non-issue.

The first co-primary efficacy endpoint will be analyzed using Fisher's exact test. Following the closed sequential procedure, the second co-primary efficacy endpoint will be analyzed using Fisher's exact test if the first co-primary endpoint is statistically significant.

The proportion of subjects who are pain-free at 2 hours postdose will be calculated as the number of subjects who are pain-free at 2 hours postdose divided by the number of subjects with non-missing assessment at 2 hours postdose. Missing primary efficacy endpoint data will be imputed using the last observation carried forward (LOCF). Results based on the LOCF data and the observed data will be displayed separately.

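### The stated 88% power for pain freedom fits an uncorrected test; the planned Fisher's exact test gives about 85.5%, which also caps power under the both-endpoints success rule

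*Protocol*

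**What the plan says.** Protocol 10.7 and SAP 3.5 carry the same sample-size argument. For pain freedom at 2 hours they assume 17.6% on placebo and 29.2% on DFN-15 and state: "A sample size of 600 subjects will provide 88% power to detect this assumed difference between placebo and DFN-15". The test is two-sided at 5%, and dropout is taken as 15%. For freedom from the Screening MBS they assume 28.2% and 44.7% and state: "A sample size of 480 subjects will provide 94% power to detect this assumed difference between placebo and DFN-15", on the same alpha and dropout. The first endpoint needs more subjects, so "the larger sample size will be used for the study", that is, 600. Neither section names the test or formula behind 88% or 94%, and neither gives the power to succeed on both endpoints.

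The analysis sections name one test. SAP 8.1.1 says: "The first co-primary efficacy endpoint will be analyzed using Fisher's exact test", and it specifies the same test for the second endpoint. Protocol 10.5.1 also uses Fisher's test for pain freedom and says that the MBS endpoint "will be similarly analyzed using Fisher's exact test". For the MBS analysis it adds that "that symptom must be present predose but does not have to be designated as the MBS at predose". On the decision rule, SAP 8.1.1 states that "statistical significance with both co-primary endpoints is required to declare trial success".

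**The concern.** Fisher's exact test is conservative with binomial data: its actual type I error is below the nominal 5%, and its power is lower than that of the uncorrected chi-square or normal test at the same sample size. A power figure from an uncorrected formula therefore overstates what Fisher's test delivers. A reader who sees 88% in the sample-size section and Fisher's test in the analysis section will take the one to describe the other.

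The success rule raises the stakes slightly. When both endpoints must be significant, the chance of success cannot exceed the smaller of the two marginal powers, so any overstatement for pain freedom carries straight into the ceiling on the chance of a successful trial. The plan shows only 88% and 94%, and a reader cannot tell that this ceiling lies below both.

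**Working it through.** **Inputs** (Protocol 10.7, SAP 3.5): two-sided alpha 0.05; 1:1 allocation; 15% dropout; pain freedom 0.176 vs 0.292 with 600 randomized; Screening MBS 0.282 vs 0.447 with 480 quoted and 600 used.

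**Subjects per arm.** Taking 15% off: 600 × 0.85 / 2 = 255 and 480 × 0.85 / 2 = 204. Dividing by 1.15 instead: 600 / 1.15 / 2 = 260.9 (260 or 261). No dropout: 300 and 240.

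**Step 1: reproduce the stated 88%.** At 255 per arm the difference is 0.292 − 0.176 = 0.116 and the mean rate is 0.234.

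- Unpooled SE = √[(0.176 × 0.824 + 0.292 × 0.708) / 255] = 0.03714. Unpooled normal power = Φ(0.116 / 0.03714 − 1.96) = Φ(1.163) = 87.8%.
- Pooled SE = √[2 × 0.234 × 0.766 / 255] = 0.03749. Pooled normal power = Φ[(0.116 − 1.96 × 0.03749) / 0.03714] = Φ(1.145) = 87.4%.
- Arcsine approximation: 87.6%.
- Uncorrected chi-square test, by enumerating all pairs of binomial outcomes: 87.6%.

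Three of the four round to 88%. The pooled formula rounds to 87% at 255 per arm and gives 88.0% at 260. The stated figure is therefore reproducible by an uncorrected method.

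**Step 2: the planned test.** Fisher power is the sum of P(x; n, p₁) × P(y; n, p₂) over all outcome pairs (x, y) whose two-sided Fisher p-value is at most 0.05.

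| Pain freedom, per arm | Dropout reading | Fisher power |
|---|---|---|
| 255 | 15% taken off | 85.46% |
| 260 / 261 | N / 1.15 | 86.0% / 86.2% |
| 300 | none | 90.7% |

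None rounds to 88%. Fisher first reaches 88% at 275 per arm (88.05%), or 550 / 0.85 ≈ 648 randomized. The shortfall at 255 per arm is 87.62 − 85.46 = 2.2 points like for like, and 88 − 85.46 = 2.5 against the stated figure. With N / 1.15 the latter is 1.8 to 2.0 points.

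**Step 3: the second endpoint.** At 204 per arm the uncorrected chi-square test gives 93.6%, which rounds to the stated 94%. Fisher gives 92.2%, a gap of 93.58 − 92.23 = 1.35 points. The trial randomizes 600, however, so the relevant Fisher values are:

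| Screening MBS, per arm analysed | Fisher power |
|---|---|
| 255 (all have the symptom predose) | 96.7% |
| 219 (86% of 255) | 94.1% |
| 218 | 93.98% |
| 215 (84% of 255) | 93.6% |
| 204 (80% of 255) | 92.2% |

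The documents give no share of subjects with the Screening MBS present predose; the 80% case is an assumption made only to show the range. The stated 94% survives at 600 down to about 219 per arm, or 215 if rounding up from 93.6% is allowed.

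**Step 4: both endpoints.** Whatever the correlation, joint power lies between (power₁ + power₂ − 1) and the smaller of the two.

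- MBS analysed in 255 per arm: 0.8546 + 0.9672 − 1 = 0.822, up to 0.855. Independence would give 0.8546 × 0.9672 = 0.827.
- MBS analysed in 204 per arm (assumed): 0.8546 + 0.9223 − 1 = 0.777, up to 0.855.

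**The case against.** The strongest case against is one of weight. Sizing by an approximation and analysing by Fisher's test is common and contradicts no sentence in either document. The sizing method is inferred, since none is named. The target is approximate, the response and dropout rates are assumptions, and neither document makes 88% a minimum. Power for pain freedom stays above 85%. All of that is fair, and it means this is a mismatch of method, not an arithmetic slip. It does not make 88% the power of the planned test. Two figures, 88% and 94%, both fit an uncorrected method and both miss under Fisher, which makes rounding an unlikely explanation.

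Second, the documents never claim joint power, and a ceiling at the smaller marginal power applies to every trial that must win on both endpoints. That is true. The lower limits also need the most adverse dependence between two outcomes in the same patients, so they are bounds and not forecasts. The ceiling of about 85.5% needs no assumption about correlation.

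Third, any restated figure is conditional too. SAP 8.1.1 excludes subjects who took rescue medication up to the 2-hour assessment and those with mild or no predose pain, while LOCF keeps some subjects whose 2-hour value is missing. The plan does not say whether the 15% covers these exclusions. This stands: 85.5% should be quoted with its 255 per arm, and 96.7% for MBS holds only if everyone analysed had the symptom predose.

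**Conclusion.** The concern holds. On the plan's own assumptions, the two-sided Fisher's exact test has about 85.5% power for pain freedom with 255 per arm, not 88%, and no dropout reading checked brings it to 88%. Under the both-endpoints rule, the power to succeed is at most about 85.5%, and between 82.2% and 85.5% if all 255 per arm contribute to the MBS analysis. The second endpoint is not short at 600 randomized unless fewer than about 215 to 219 per arm have the Screening MBS predose.

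The effect is small, at 2 to 2.5 points. Type I error, the validity of the analysis and the success decision are unaffected. The conclusion rests on the assumed response rates, equal arms and the 15% dropout. That the 88% came from an uncorrected method is an inference from the fit; the Fisher figures do not depend on it. It should be fixed because a headline design figure does not describe the planned primary test and the correction costs almost nothing.

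**What to change.** In Protocol 10.7 and SAP 3.5, name the two-sided Fisher's exact test as the basis for power and restate the figures with the numbers they rest on: about 85% (85.46%) for pain freedom at 255 per arm; for Screening MBS, about 97% if all 255 per arm have the symptom predose and about 92% at 204 per arm, with that share labelled as an assumption.

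Add one sentence: because both co-primary endpoints must be significant, the power to meet the success rule is at most about 85.5% (82.2% to 85.5% whatever the correlation if all 255 per arm can be analysed for MBS, with a lower minimum if fewer can).

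This changes the wording of two sections and leaves enrolment and the test as they are. The only cost is that the stated power for pain freedom falls by about 2 to 2.5 points.
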